where π_{COMP-I} is the true rate of the composite of all-cause death and all stroke in the Intervention arm and π_{COMP-C} is the true rate of the composite of all-cause death and all stroke in the Control arm.

The null hypothesis will be tested at a one-sided 0.025 level of significance using a two-sample z-test of proportions.

- **CNS infarction** (NeuroARC defined) [evaluated at 30 days in the eITT analysis population]

The hypothesis is that the event rate for CNS infarction in the Intervention Group at 30 days will be lower than the Control Group at 30 days.

The formal null and alternative hypotheses to be tested are:

$$H_0: \pi_{CNS-I} = \pi_{CNS-C}$$

$$H_1: \pi_{CNS-I} < \pi_{CNS-C}$$

where π_{CNS-I} is the true rate of CNS infarction in the Intervention arm and π_{CNS-C} is the true rate of CNS infarction in the Control arm.

The null hypothesis will be tested at a one-sided 0.025 level of significance using a two-sample z-test of proportions.

- **Total volume of cerebral ischemic lesions** detected by DW-MRI, [evaluated 2 to 5 days post-procedure in the efficacy Intention to Treat (eITT) analysis population]

The hypothesis is that the total volume of cerebral ischemic lesions in the Intervention Group will be lower than the Control Group.

The formal null and alternative hypotheses to be tested are:

$$H_0: \pi_{TLV-I} = \pi_{TLV-C}$$

$$H_1: \pi_{TLV-I} < \pi_{TLV-C}$$

where π_{TLV-I} is the true total volume of cerebral ischemic lesions in the Intervention arm and π_{TLV-C} is the true total volume of cerebral ischemic lesions in the Control arm.

The null hypothesis will be tested at a one-sided 0.025 level of significance using the two-sample z-test.

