12.2.4.1.2 Primary Efficacy Endpoint

Sample size for assessing superiority of Intervention over Control with respect to the hierarchical composite primary efficacy endpoint was estimated using the following assumptions:

- All-cause mortality or any stroke at 30 days will occur in ~11% of Control subjects and ~6% of Intervention subjects (5% absolute reduction, ~45% relative reduction)
- Among subjects without all-cause mortality or any stroke to 30 days, NIHSS worsening 2-5 days post-procedure will occur in 9% of Control subjects and 6% of Intervention subjects (3% absolute reduction, 33.3% relative reduction)
- Among subjects without all-cause mortality or any stroke to 30 days and without NIHSS worsening 2-5 days post-procedure, MRI findings will occur in 89% of Control subjects and in 73% of intervention subjects (16% absolute reduction, 17.9% relative reduction).
- Among subjects without all-cause mortality or any stroke to 30 days, without NIHSS worsening 2-5 days post procedure, but with MRI findings, lesion volumes can be divided into 3 out of 4 subsets- 0 mm³, >0-50 mm³, >50-150 mm³ and >150 mm³. For these volume subsets, we expect rates of 11%, 7%, 33% and 48%, respectively, in the control group and 27%, 19%, 7.5%, and 46%, respectively, in the intervention group.
- For sample size calculations a relative reduction of 30% is expected in each lesion volume subset, based on the comparison of total lesion volumes between device and control groups in DEFLECT I, MISTRAL C⁷³ SENTINEL⁹ and CLEAN-TAVI⁷⁴.
- The smallest detectable difference in MRI is a single voxel. In addition, inter-rater mean differences between two independent observers was 15% or ~5 voxels (40.5 mm³) in the KSH Methodology/Reproducibility Study (data on file). Accordingly, a meaningful difference to declare a win/lose between MRI lesion volumes was set at a 15% relative difference or a 50 mm³ absolute difference.

- Loss to post-procedure DW-MRI follow-up is expected to occur in 15% of all subjects (due to contraindications to post-procedure DW-MRI [e.g., pacemaker implantation] or subject non-compliance)
- Loss to follow-up for all other reasons is expected to be 5%.
- Overall α (one-sided)=0.025; (see §12.4.2)

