To determine the required sample size, calculations were performed by simulating 5000 samples on SAS software postulating the above parameters; mortality and stroke rates and proportions of patients with NIHSS worsening, any MRI lesions and volumes divided to subsets were simulated by a random binary function.

An evaluable sample size of 225 subjects (2:1 randomization with 150 in the Intervention group and 75 new Control subjects) is sufficient to demonstrate superiority of the Intervention group to the Control group for the primary efficacy endpoint when pair-wise comparisons are made between subjects using the Finkelstein-Schoenfeld method,² and outcomes between treatment groups are compared by the chi-square test.

Therefore, the initial randomized cohort sample size of 225 subjects (150 in the Intervention group and 75 new control subjects) will have >80% power to demonstrate superiority of the Intervention group for the primary efficacy endpoint (one sided $\alpha=0.025$). Notably, in several simulations, considering different distributions for lesion volume and different distributions for death/ stroke, the study power remained greater than 80%.

Adding the 63 control subjects already enrolled in REFLECT Phase I for a total of 138 control subjects would increase the power to at least 92% to demonstrate superiority of the primary efficacy endpoint. 5% loss to follow up is included.

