No imputation of missing DW-MRI data will be performed for the primary analysis. However, in order to assess the sensitivity of results to missing DW-MRI data, multiple imputations with the linear regression approach will be used as the secondary sensitivity analysis. This assessment is necessary because the rate of permanent pacemaker implantation (causing loss to DW-MRI follow-up) may vary according to patient clinical characteristics and prosthesis type.¹⁰⁶ Specifically, missing total volume of cerebral ischemic lesions on post-procedure diffusion-weighted MRI will be imputed via multiple imputation linear regression (10 imputed data sets will be created). The covariates used for the imputation model will be treatment group, age at time of enrollment, body mass index, race, smoking status, creatinine level, hyperlipidemia, hypertension, aortic arch disease burden, porcelain aorta, aortic valve area at baseline, procedure time, country, valve type, balloon post dilatation, arch type, and level of calcification. This creation of the 10 datasets will be carried out using PROC MI in SAS. For each data set, the above-mentioned chi-square test will be carried out on the primary endpoint and one overall chi-square result will be generated from the 10 datasets. For each patient with missing TLV, the crux of multiple imputation is to estimate TLV from patients with non-missing TLV who have similar baseline characteristics as the patient with missing TLV. Thus, in essence, TLV for high risk patients with missing TLV due to pacemaker will theoretically be estimated from patients with similar high risk profiles who do not have pacemakers.

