In the final analysis, assessment of treatment-by-study-center and treatment-by-region on the primary efficacy endpoint will be carried out on the eITT population using quantile regression. Total score obtained for each subject using the proposed approach (Finkelstein and Schoenfeld) will be the model dependent variable. The following two models will be built: 1.) Model inclusive of treatment, study center, and treatment-by-study center interaction, and 2.) Treatment region (US versus OUS, Phase I only), and treatment-by-region interaction. A 0.15 level of significance will be used to assess the significance of each of the study center and region effects on the efficacy endpoint. A non-significant result for each of study center and region will support the pooling of patients across study centers and across regions for the primary efficacy analysis. A significant result will require further inspection of the by-center and by-region results to assess if poolability is appropriate. Note that centers with less than 5 subjects will be pooled with other centers by closest geographic region; this pooling will be carried out prior to the unblinding.

Additionally, an assessment of treatment-by-study-center and treatment-by-region on each component of the primary efficacy endpoint will be carried out on the eITT population using analysis of variance on the cube root transformation for total lesion volume data and logistic regression for death/stroke and NIHSS worsening, with effects for 1.) Treatment, study center, and treatment-by-study center interaction, and 2.) Treatment, region (US versus OUS, Phase I only), and treatment-by-region interaction. As above, a 0.15 level of significance will be used to assess the significance of the interaction; a non-significant interaction or an interaction that is significant but only quantitative (and not qualitative) in nature will support the pooling of patients across study centers and across regions for the primary analysis; and centers with less than 5 subjects will be pooled with other centers by closest geographic region, with pooling carried out prior to the unblinding.

In addition, the above analysis will be repeated in the eITT population (separately in Phase I and Phase II analysis sets) to assess the consistency of treatment effects on each component of the primary efficacy endpoint across the following variables:

- Subject gender (male versus female)
- Valve prosthesis type (Edwards vs. Medtronic)

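### Total lesion volume has many zeros and a long right tail, but its gated test is an untransformed z-test and its sensitivity imputation is a linear regression with no zero or bound handling

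*Combined protocol and SAP*

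**What the plan says.** Section 12.2.1.1.3 lists five hypothesis-driven secondary endpoints, tested in a fixed order once both primary endpoints are met. Total lesion volume is last. The hypothesis concerns a quantity that "is the true total volume of cerebral ischemic lesions in the Intervention arm", and likewise in the Control arm. Whether that is a mean, a median or a mean on another scale is not stated. The test is given as: "The null hypothesis will be tested at a one-sided 0.025 level of significance using the two-sample z-test".

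Section 12.4.3 deals with missing DW-MRI for the hierarchical primary endpoint. The primary analysis imputes nothing. In a secondary sensitivity analysis, missing total volume "will be imputed via multiple imputation linear regression (10 imputed data sets will be created"), and the primary test is then rerun on each data set. No transformation, lower bound or separate model for zero volume is given.

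Elsewhere the plan does not treat this variable as normal on its raw scale. Section 12.4.3 examines centre and region effects "using analysis of variance on the cube root transformation for total lesion volume data". The Phase I interim simulations in the same section assume a negative binomial distribution. Section 12.4.5.1.2 lets the observed distribution decide the adjusted model for imaging endpoints.

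**The concern.** A z-test on raw means gives most weight to a few very large lesion volumes. The device is expected to act partly by leaving more patients with no lesion at all, and a difference in means registers that weakly when the variance comes from the upper tail. A rank test or a cube-root scale registers it much better. At stake is power for the only formal volume claim.

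The imputation raises a different issue, closer to the primary endpoint. A linear regression with normal errors produces a continuous, unbounded variable. Tier 3 asks whether volume is exactly zero, and Tier 4 compares positive volumes. Imputed values that are never zero and sometimes negative fit neither tier, and the plan has no rule for scoring them. This is the named check on missing scans, where "Loss to post-procedure DW-MRI follow-up is expected to occur in 15% of all subjects".

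**Working it through.** **Inputs from the protocol**
- Allocation (12.2.4.1.2): "2:1 randomization with 150 in the Intervention group and 75 new Control subjects", or 138 controls if Phase I controls are pooled.
- Scans after 15% MRI loss: 150 × 0.85 ≈ 128 device; 75 × 0.85 ≈ 64 control; 138 × 0.85 ≈ 117 pooled control. The further 5% general loss is not applied here.
- Zero volume: 11% control, 27% device (12.2.3, Table 11b).
- Effect on volume: 30% relative reduction in each subset (12.2.4.1.2).
- Unprotected TAVI, weighted averages: 2.18, SD 4.5 cm³ (Table 4); 1.49, SD 2.18 cm³ with strokes excluded (Table 5). First-generation device: 0.77, SD 0.96 cm³ (Table 6).
- Skew: one patient-level series in Table 4 has mean 4.3, SD 14.9 and median 0.30 cm³.

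**The plan's own figure.** No power is stated for the volume test. The nearest figure is for the hierarchical primary endpoint: over 80% with 75 controls and at least 92% with 138. I simulated that test (event days, NIHSS steps and within-category volumes assumed). With the 30% reduction included, power was 81–84% and 93–94%, matching the plan. Without it, power was 54–60% and 71–75%. The plan's working effect is therefore the category table and the 30% reduction together.

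**Raw z-test, 30% reduction only, equal SDs.** Power = Φ(δ/SE − 1.96), with SE = SD × √(1/64 + 1/128) = SD × 0.1531.
- Table 4: δ = 0.3 × 2.18 = 0.654; SE = 0.689; Φ(0.949 − 1.96) = 15.6%.
- Table 5: δ = 0.3 × 1.49 = 0.447; SE = 0.334; Φ(1.339 − 1.96) = 26.7%.

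**Three tests on the same data.** The control arm has 11% zeros and a lognormal positive part, matched to the overall mean and SD. For Table 4 the positive-part mean is 2.18/0.89 = 2.449, and the log-variance is ln[((4.5² + 2.18²)/0.89)/2.449²] = 1.54. Both tests are unaffected by units, so what matters is SD/mean and shape. Power at one-sided 0.025, 3,000 trials per setting, shown as Table 4 / Table 5 moments:

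| Scenario | Scans (control v device) | Raw z | Wilcoxon | Cube-root z |
|---|---|---|---|---|
| Zeros 11% v 27% plus 30% reduction | 64 v 128 | 40% / 64% | 86% / 91% | 87% / 92% |
| Same, pooled controls | 117 v 128 | 60% / 82% | 96% / 98% | 96% / 98% |
| 30% reduction only | 64 v 128 | 17% / 30% | 30% / 41% | 26% / 32% |
| Zeros differ only | 64 v 128 | 7% / 11% | 44% / 46% | 49% / 59% |

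Repeat runs with other seeds moved these by a point or so. In the combined scenario they gave raw z 39–65% and Wilcoxon 85–92% at 64 v 128, and about 59–82% and 95–98% with pooled controls.

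**Type I error.** With no difference between arms, 64 v 128 scans and a nominal 2.5%, the raw z-test rejected in favour of the device in about 1–1.7% of trials. Wilcoxon gave 2.2–2.8%.

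**Imputation.** The share of negative draws from an unbounded normal is Φ(−mean/SD):
- Table 4: Φ(−2.18/4.5) = 31%.
- Table 5: Φ(−1.49/2.18) = 25%.
- First-generation device: Φ(−0.77/0.96) = 21%.

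The probability of an exact zero is nil, against an expected 11–27%.

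**The case against.** Several points on the other side stand.

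- A reader might infer that the z-test has almost no power, because simulating from the Table 11b categories alone can give figures of a few per cent. The documents do not support that. It leaves out the 30% reduction, and it depends on the tail above 150 mm³, which the protocol does not describe. With categories plus reduction at 117 v 128 scans, z-test power ran from 87% to 26% to 9% as I made the assumed tail heavier. With the first-generation device moments, a normal approximation gives 70–71% at 64 v 128 and 91% with pooled controls.
- A reader might infer a false-positive risk. There is none in the tested direction, where the z-test is conservative.
- A reader might infer that the gated volume test uses imputed values. It does not: imputation is specified only for the sensitivity analysis of the hierarchical endpoint.
- A reader might take the cube root in section 12.4.3 as an admission that the raw scale is unsuitable. The section gives no reason for it.
- The volume test is fifth in sequence. At 75 v 150 the NIHSS gate (9% v 6%) has about 14% power. The stroke gate has about 18% if the 30-day rates in Table 11a for the largest trial (9.09% v 5.63%) applied at 7 days. The volume test may seldom be reached formally.
- The absence of a transformation or bound is read from silence, and section 12.1 defers some detail to a SAP. Setting negative draws to zero would create lesion-free subjects, but their share would follow from the SD/mean ratio and not from how often patients are lesion-free.

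These points limit the size and urgency. They leave the efficiency loss and the mismatch between the imputation model and Tier 3 in place.

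**Conclusion.** The point holds at moderate severity, as a cheap improvement. Under the plan's combined assumptions, Wilcoxon gains roughly 27–46 percentage points of power over the z-test at 64 v 128 scans, and roughly 16–36 points with pooled controls. A cube-root test does about as well as Wilcoxon. In the imputation, about one draw in five to one in three would be negative and none zero, which makes the sensitivity analysis a poor check on Tiers 3 and 4.

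This rests on a lognormal positive part, on SD/mean ratios from historical series, and on applying the 11% and 27% zero shares to every scanned subject. The plan states those shares for subjects without death, stroke or NIHSS worsening. Strokes remain in the eITT population, and more of them are expected in controls, so their volumes could add signal to a comparison of means. The negative shares use marginal moments. The imputation covariates would change the percentage but would not create zeros.

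**What to change.** **Test.** In section 12.2.1.1.3, state the parameter and replace the z-test with a one-sided Wilcoxon rank-sum test at 0.025, or with a test on the cube-root scale already used in section 12.4.3. Report medians alongside means. A Hodges-Lehmann shift should not be the main estimate, given the ties at zero.

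**Imputation.** In the section 12.4.3 sensitivity analysis, impute in two parts: any lesion by logistic regression, then positive volume by predictive mean matching among those with a lesion. Score Tiers 3 and 4 only after both steps. PROC MI, which the plan already names, can do both.

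**Cost.** SAP wording and a few lines of code, settled before unblinding. The volume test would no longer target a difference in means. Sample size, data collection and the testing order are unchanged.

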12.2.2 Expected Control Primary Safety Endpoint Event Rate

An expected event rate for the control group was determined based on published data from subjects undergoing unprotected TAVI.

A search of bibliographic scientific databases (PubMed and EMBASE) was undertaken to identify studies reporting VARC combined safety outcomes using the following search parameters:

- Language = English, species = humans
- Publication date January 2011 (publication of original VARC definitions) to present
- Keywords included: Valve Academic Research Consortium or VARC; aortic valve; and percutaneous, transcatheter, transluminal, transarterial, transfemoral, or transapical

Results were evaluated according to the following selection criteria:

- Peer-reviewed publications only. Abstracts, case reports, conference presentations, editorials, and expert opinions were excluded.
- Reported using VARC or VARC-2 definitions (explicitly mentioned in text), and reported VARC combined safety endpoint or the VARC-2 early safety endpoint at 30 days
- $N \geq 20$ (studies reporting outcomes in fewer than 20 TAVI subjects were excluded)
- Patients with severe AS undergoing TAVI with Medtronic or Edwards valves. Studies reporting outcomes exclusively in valve-in valve or subjects undergoing TAVI via any approach other than transfemoral or transapical (e.g., transaxillary, transsubclavian, direct aortic) were excluded. When larger cohorts included these subjects, the results in these subjects were excluded when data allowed; otherwise they were included.
- Publications with overlapping data were identified where possible, and the most recent procedural timeframe (or largest N) was used and the other(s) discarded.

Additional relevant studies were identified through a manual search of secondary sources, including the bibliographies of initially identified articles and review articles and commentaries.

Although the primary safety endpoint is the VARC-2¹ early safety endpoint, which differs from the original VARC definition⁷⁸, studies reporting either composite endpoint were collected and

evaluated to inform determination of the PG. Based on differences between the definitions (see Table 9 below), we would expect the VARC-2 event rate to be slightly higher based on the addition of all stroke and Stage 2 acute kidney injury; however, more published data according to the earlier VARC definitions is likely available.

Table 9. Comparison of VARC and VARC-2 Early Safety Endpoint Components

VARC⁷⁸ Combined Safety Endpoint (at 30 days)	VARC-2¹ Early Safety (at 30 days)

 • All-cause mortality • Major stroke • Life-threatening (or disabling) bleeding • Acute kidney injury – Stage 3 (including renal replacement therapy) • Coronary artery obstruction requiring intervention • Major vascular complication • Repeat procedure for valve-related dysfunction (surgical or interventional therapy) • Peri-procedural MI 	
 • All-cause mortality • All stroke (disabling and non-disabling) • Life-threatening bleeding • Acute kidney injury – Stage 2 or 3 (including renal replacement therapy) • Coronary artery obstruction requiring intervention • Major vascular complication • Valve-related dysfunction requiring repeat procedure (BAV, TAVI, or SAVR)
Note: Bold text indicates differences between the two definitions. This table represents an overall comparison; details of individual component definitions have also changed between consensus documents.	

The literature search and sift identified a total of 19 studies reporting the original VARC combined safety endpoint and 6 studies reporting the VARC-2 early safety endpoint (Table 10 below).

Table 10. Published Combined Safety Event Rates at 30 days after Unprotected TAVI

Study	N	Event Rate (%)
VARC 1 Combined Safety		
Abdel-Wahab 2012 ⁷⁹	70	13.0
Buchanan 2011 ⁸⁰	305	38.2
D'Ascenzo 2013 ⁸¹	377	28.9
Dubois 2013 ⁸²	73	29.0
van der Boon 2014 ⁸³	882	26.6
Eltchaninoff 2012 ⁸⁴	190	16.3
Gurvitch 2011 ⁸⁵	310	18.4
Hammerer 2012 ⁸⁶	50	18.0
Hayashida 2012 ⁸⁷	260	17.3
van der Boon 2013 ⁸⁸	298	23.5
Scherner 2012 ⁸⁹	150	28.0
Seiffert 2013 ⁹⁰	326	21.2
Stahli 2011 ⁹¹	130	20.8
Ussia 2012 ⁹²	181	25.8

Wenaweser 2011 ⁹³	256	29.3
Yamamoto 2013 ⁹⁴	415	16.4
Abramowitz 2014 ⁹⁵	249	6.8
Greif 2014 ⁹⁶	461	12.6
Sabate 2013 ⁹⁷	1416	14.0
Simple mean	337	23.8
Weighted mean	--	20.4
VARC 2 Early Safety		
D'Onofrio 2013 ⁹⁸	774	21.7
Tarantini 2013 ⁹⁹	250	21.2
Chopard 2014 ¹⁰⁰	3928	40.4
Conradi 2013 ¹⁰¹	100	19.0
Magri 2013 ¹⁰²	330	30.9
Seco 2014 ¹⁰³	32	21.9
Simple mean	902	25.9
Weighted mean	--	35.8

The above studies represent the best estimation of the expected event rate in the population of subjects with severe AS undergoing TAVI via the transfemoral or transapical route with Edwards or Medtronic valve systems. The average event rate in studies reporting outcomes according to the VARC-2 definition (the primary safety endpoint for the REFLECT Trial) was 25.9%; among studies reporting the slightly more circumscribed VARC 1 definition, the average event rate was 23.8%. Therefore, the expected event rate of the primary safety endpoint in the Control group was estimated at 25%.

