12.2 Sample Size Calculation

12.2.1 Hypotheses

12.2.1.1.1 Primary Safety Hypothesis (Phase I and Phase II reported individually)

The primary safety hypothesis is that the rate of the primary safety endpoint (a composite of death, stroke, life-threatening or disabling bleeding, AKI [Stage 2 OR 3], coronary artery obstruction requiring intervention, major vascular complication, and valve-related dysfunction requiring repeat procedure) in the group undergoing TAVI with either protection device system (Intervention Groups) at 30 days will be less in each device group (TriGuard HDH and TriGUARD 3) compared separately to a performance goal (PG) of 34.4%.

Specifically, the primary safety analysis will assess if the Intervention group's safety event rate is significantly less than the PG of 34.4% using a one-sample z-test of proportions. The formal null and alternative hypotheses to be tested are:

$$H_0: \pi \geq 0.344$$

$$H_1: \pi < 0.344$$

where π is the true safety event rate for the Intervention arm.

The primary hypothesis test will be carried out by comparing the upper bound of the one-sided 95% confidence interval of the primary safety endpoint event rate in the intervention arm to the PG. With the planned evaluable sample size of 179 subjects and a one-sided alpha of 0.05, the critical value for rejection of the null hypothesis is 28.5%: if the primary

safety endpoint occurs in 28.5% or less of intervention group subjects, the performance goal will be met.

After accounting for a potential 5% loss to clinical follow-up at 30 days (including subjects who do not meet As Treated population criteria), the total required intervention group sample size is 190 subjects in each Phase. For Phase II 150 subjects randomized to the TriGUARD 3 and the 40-50 roll-ins will constitute the primary safety population.

Trial success depends on both primary endpoints being met in their primary analysis populations; i.e., the primary safety endpoint must be met in the primary (AT) population and the primary efficacy endpoint must be met in the primary (eITT) population in order for the trial to be declared a success. Because both primary endpoints (safety and efficacy) must be met (i.e., both H_0 must be rejected) for the trial to be declared a success, no adjustment to alpha for multiple endpoints is required for the two primary study endpoints.

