12.2.4 Sample Size Estimation

12.2.4.1 Primary Safety Endpoint

The primary safety endpoint is combined safety (VARC-2 defined as a composite of death, stroke, life-threatening or disabling bleeding, acute kidney injury [Stage 2 or 3], coronary artery obstruction requiring intervention, major vascular complication, and valve-related dysfunction requiring repeat procedure), evaluated at 30 days.

Based on published literature of patients undergoing unprotected TAVI (§12.2.2), establishing the expected Control event rate of 25%, and a 37.5% relative margin (absolute delta 9.4%), a Performance Goal (PG) has been set at 34.4% (25% + 9.4%). The primary safety analysis will assess if the Intervention group's safety event rate is significantly less than the PG of 34.4%.

A sample size of 179 evaluable subjects in the intervention group will provide 85% power to determine whether the intervention group meets the PG at the one-sided $\alpha=0.05$ level when using a one-sample z-test of proportions. After accounting for a potential 5% loss to clinical follow-up or dropout from the primary analysis population (As Treated) at 30 days, the total required sample size is 190 subjects in each intervention group. Therefore, the initial randomized sample size of 190 subjects in each intervention group in each phase will have sufficient power to determine whether the intervention meets the safety PG. For Phase II 150 subjects randomized to the TriGUARD 3 and 40- 50 roll-ins will constitute the primary safety population.

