12.4.2 Primary Safety Endpoint

The primary safety hypothesis is that the rate of the Combined Safety Endpoint (defined according to VARC 2 as the composite of death, stroke, life-threatening or disabling bleeding, AKI [Stage 2/3], coronary artery obstruction requiring intervention, major vascular complication, and valve-related dysfunction requiring repeat procedure) at 30 days in the group undergoing TAVI with the TriGuard HDH or TriGUARD 3 system (Intervention group) is significantly less than the Performance Goal (PG). The following analysis will be carried out in the AT (primary analysis population) and ITT populations including Roll-ins.

The primary safety analysis will assess if the Intervention group's safety endpoint rate is significantly less than 34.4% using a one-sample z-test of proportions. Specifically, the null and alternative hypotheses to be tested are:

$$H_0: \pi \geq 0.344$$

$$H_1: \pi < 0.344$$

where π is the true, unknown, safety event rate for the Intervention arm.

The number and percentage of patients in each group experiencing the safety endpoint rate will be presented for each treatment; in addition, one-sided 95% confidence intervals of the percentage will be presented, based on the normal approximation to the binomial distribution. For the intervention group, the above null hypothesis will be carried out at a one-sided 0.05 level of significance using the one-sample z-test of proportions. Only AT and ITT patients who experienced a safety endpoint or had at least 23 days (30 days minus the allowable 7 day visit window) of follow-up will be included in the analyses.

As a secondary analysis, to account for any missing data in the primary endpoint (caused by not experiencing the safety endpoint AND prematurely withdrawing from the study before 23 days of follow-up), a tipping point analysis will be conducted. Here the above safety null hypothesis will be repeatedly tested, first assuming 0 patients with missing data failed (i.e., experienced the safety event), then assuming 1 patient with missing data experienced the safety event, then assuming 2 patients with missing data experienced the safety event, etc. Of interest is the "tipping" point, i.e., the number of Intervention missing data subjects who must be imputed as failures in order for the safety null hypothesis to no longer be rejected.

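### One of the two means cited for the 25% expected safety rate is miscalculated (21.3%, not 23.8%), and the safety test is stated as two rules that can differ by one event

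*Combined protocol and SAP*

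**What the plan says.** **Expected rate and goal.** Section 12.2.2 reports "a total of 19 studies reporting the original VARC combined safety endpoint and 6 studies reporting the VARC-2 early safety endpoint", with the rates listed in Table 10. The text then gives the VARC-2 mean ("the primary safety endpoint for the REFLECT Trial) was 25.9" per cent) and the VARC-1 mean ("among studies reporting the slightly more circumscribed VARC 1 definition, the average event rate was 23.8" per cent). From these it concludes that "the expected event rate of the primary safety endpoint in the Control group was estimated at 25" per cent. Section 12.2.4.1 adds a 37.5% relative margin: "a Performance Goal (PG) has been set at 34.4% (25% + 9.4" per cent).

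**Decision rule.** Section 12.2.1.1.1 specifies a one-sample z-test of proportions against 34.4% at one-sided 0.05. It then says that the test is done by "comparing the upper bound of the one-sided 95% confidence interval of the primary safety endpoint event rate in the intervention arm to the PG". For 179 evaluable subjects it states that "the critical value for rejection of the null hypothesis is 28.5" per cent. Section 12.4.2 describes the one-sided 95% intervals as "based on the normal approximation to the binomial distribution" and again assigns the hypothesis test to the z-test.

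**Sample size.** Section 12.2.4.1 plans 179 evaluable subjects, or 190 before 5% loss. The Phase II safety population is 150 randomized device subjects plus 40 to 50 roll-ins, that is 190 to 200 before loss.

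**The concern.** The safety endpoint is co-primary: the trial succeeds only if both the safety and the efficacy tests are met. Its threshold is a fixed number justified by a literature average, so that average should follow from the table it cites. The VARC-1 figure does not.

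The rule for meeting the threshold should also give one answer for any result. A z-test of a proportion normally uses the variance under the null value. A normal-approximation confidence bound normally uses the variance at the observed rate. For observed rates below 34.4% the second variance is smaller, so the bound is the more lenient rule. If the two give different answers for the count actually seen, the choice between them would be made after the data are known.

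**Working it through.** **1. VARC-1 mean (Table 10, 19 rows).**
Rates: 13.0, 38.2, 28.9, 29.0, 26.6, 16.3, 18.4, 18.0, 17.3, 23.5, 28.0, 21.2, 20.8, 25.8, 29.3, 16.4, 6.8, 12.6, 14.0.
- Sum = 404.1. Simple mean = 404.1/19 = 21.27%. Printed: 23.8%.
- Mean N = 336.8. Printed: 337. Reproduces.
- N-weighted mean = 20.37%. Printed: 20.4%. Reproduces.

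Because the same 19 rows reproduce the other two summaries, the rows appear intact and the fault lies in 23.8% alone. Dropping any one, two or three studies does not give 23.8%. Dividing by 17 does (404.1/17 = 23.77), which is a possible cause but not a proven one.

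**2. VARC-2 mean (6 rows).**
Simple mean 25.85% (printed 25.9%), weighted mean 35.76% (printed 35.8%), mean N 902. All reproduce.

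**3. Effect on the goal.**
The plan's own step reproduces: 25% × 1.375 = 34.4%. There is no formula for the 25%, so the effect of the correction depends on an assumption:
- 25% as the midpoint of the two simple means: (25.85 + 21.27)/2 = 23.6%, and × 1.375 = 32.4%.
- 25% resting on the VARC-2 mean alone: 25.9% + 9.4 points = 35.3%, or 25.9% × 1.375 = 35.6%. The existing 34.4% lies below both.

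**4. The two decision rules.**
- z-test: success if (x/n − 0.344)/√(0.344 × 0.656/n) < −1.645.
- Wald bound: success if p + 1.645√(p(1−p)/n) < 0.344, with p = x/n.

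The plan's critical value first. At n = 179 the z-test limit is 0.344 − 1.645 × 0.0355 = 28.56%, so at most 51 events (51/179 = 28.49%). This matches the stated 28.5%. The corresponding Wald limit is 28.83%, which also allows 51 events.

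At n = 190 with 55 events (28.95%):
- z = (0.2895 − 0.344)/0.03446 = −1.58: fails.
- Upper bound = 0.2895 + 1.645 × 0.0329 = 34.36%, below 34.4%: passes.

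Exact type I error is the binomial probability of meeting the limit at a true rate of 34.4%:

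| n | z-test limit | exact error | Wald limit | exact error |
|---|---|---|---|---|
| 179 | 51 | 5.5% | 51 | 5.5% |
| 190 | 54 | 4.7% | 55 | 6.5% |
| 200 | 57 | 4.5% | 58 | 6.1% |

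The limits differ at 10 of the 22 sizes from 179 to 200 and at 38 of the 81 from 170 to 250. The difference is always one event, with the Wald bound more lenient. Over 170 to 250 the exact error is 4.8% to 6.6% for the bound and 4.2% to 5.7% for the z-test.

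**5. An exact binomial rule, for comparison.**
At most 50 of 179 (exact error 3.9%, power 84.0% at a true 25%) or 54 of 190 (4.7%, power 87.9%).

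**The case against.** **On the goal.** A reader might infer that the goal itself is wrong and should fall to 32.4%, with 47 rather than 51 events allowed at n = 179 under the z-test. The documents do not support that. The midpoint is only one way to reach 25%. The VARC-2 mean is for the trial's own endpoint, it reproduces, and it lies above 25%. Section 12.2.2 itself expects VARC-2 rates to be slightly higher than VARC-1 rates, so a lower VARC-1 mean does not refute 25%. The VARC-2 weighted mean of 35.8% points upward. This objection stands: what is shown is a wrong supporting figure, not a wrong goal.

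**On the rules.** The documents name neither variance. A score bound, or a z-test using the sample variance, would remove the conflict. Section 12.4.2 describes the interval as something to be presented and gives the test to the z-test, so only one sentence in Section 12.2.1.1.1 makes the bound decisive. The rules agree at the planned evaluable size. The stated 28.5% cut would also settle the example at 190, since 55/190 is above it. Most of this stands and limits the weight of the point.

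It does not dispose of it. That one sentence says how the primary test is carried out. The 28.5% figure is tied to n = 179 and is not a general rule: it equals the z-test limit at n = 200 (57/200), but at n = 185 the z-test allows 53 events and a fixed 28.5% allows 52. The evaluable number is also not fixed at 179: 200 treated less 5% is 190.

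A reader might also take the exact errors above 5% as a fault of the z-test. For the z-test they are the ordinary effect of discrete counts.

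**Conclusion.** The point holds in two limited parts.

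1. The VARC-1 simple mean is 21.3%, not 23.8%. This is certain from Table 10. It removes part of the stated support for 25%, and hence for 34.4%, but does not by itself fix a different goal. The values 23.6% and 32.4% follow only if 25% was meant as a midpoint.

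2. The success rule is not unique as written. Assuming a null-variance z-test and a Wald bound, the gap is at most one event. It is absent at 179 and present at 38 of the 81 sizes from 170 to 250. At 190 it means an exact type I error of 4.7% or 6.5%, depending on which sentence is followed. The stated 28.5% fits the null-variance z-test.

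The gap is small, but it concerns the pass/fail line of a co-primary endpoint and costs little to close.

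**What to change.** - Correct 23.8% to 21.3% in Table 10 and in the closing text of Section 12.2.2.
- State how 25% was chosen, for example from the VARC-2 mean of 25.9% alone, and keep 34.4%. Lowering the goal is not shown to be needed. It would not be a mere text change either, because 34.4% applies separately to both devices and Phase I enrollment has ended.
- In Sections 12.2.1.1.1 and 12.4.2, name one decision rule, applied at the actual As Treated sample size, and compute the confidence interval by the matching method. Either of these would do:
  - the null-variance z-test: at most 51 of 179 or 54 of 190, consistent with the stated 28.5%, exact error 5.5% at 179;
  - an exact one-sided 95% binomial bound: at most 50 of 179 (power 84%) or 54 of 190 (power 88%).
- Say that 28.5% illustrates the rule at n = 179.

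The cost is a text correction and one test definition, with no added subjects. The z-test option leaves the planned test and critical value as they are. The exact option gives about 1 point less than the stated 85% power at n = 179. Against the exact power of the 51-event limit (87.7%), the loss is 87.7 − 84.0 = 3.7 points. At 190 the exact and z-test limits coincide, so nothing is lost there.
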